#### 6. DOSE MODIFICATIONS

Detectable systemic levels of remetinostat after topical application for 8 weeks are not anticipated. Treatment with topical remetinostat may be interrupted or dose modified as detailed below. Subjects who require discontinuation of treatment for any reason will go

off-study. The Study Doctor will assess and determine if an individual subject needs to be taken off the study due to side effects.

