The investigator has the right to discontinue a patient from study drug or withdraw a patient from the study at any time. In addition, patients have the right to voluntarily discontinue study drug or withdraw from the study at any time for any reason. Reasons for discontinuation of study drug or withdrawal from the study may include, but are not limited to, the following:

- Any subject who presents at screening or during treatment with a large (> 20 mm) SCC lesion: such a lesion will be discontinued from treatment (if applicable) and referred for evaluation for surgical resection. (If the patient has other, smaller lesions, these smaller lesions may be considered for enrollment in the study.)
- Subject withdrawal of consent at any time
- Any medical condition that the investigator or Sponsor determines may jeopardize the patient's safety if he or she continues in the study
- Investigator determines it is in the best interest of the patient
- Surgical or other treatment of target SCC before Week 8
- Pregnancy

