**Table 1: Dose Modification** 

Grade of Local Dermal Irritation	Defining Clinical Signs	Proposed Treatment Modification			
0 (No Reaction)	None				
1 (Mild)	Definite pink to red coloration	No action required; observation			
2 (Moderate)	Increased redness, with or without edema				
3 (Moderately Severe)	Very red, with edema and vesiculation	Treatment must be suspended until irritation improves to Grade 2 or lower (this must occur within 2 weeks). After the irritation improves to Grade 2 or lower, treatment may be re-started, initially TID every second day, then increased to TID daily, if tolerated. If dermal irritation does not improve to Grade 2 or lower after 2 weeks, treatment should be discontinued, and the patient withdrawn. If event re-occurs, consider discontinuation of treatment.			
4 (Severe)	Deep red, swelling and edema with bullae formation and necrosis	Treatment must be suspended until irritation improves to Grade 2 or lower (this must occur within 2 weeks). After the irritation improves to Grade 2 or lower, treatment may be re-started, initially TID every second day, then increased to TID daily, if tolerated. If dermal irritation does not improve to Grade 2 or lower after 2 weeks, treatment should be discontinued, and the patient withdrawn. If event re-occurs, consider discontinuation of treatment.			

Treatment may be stopped approximately 2 weeks before surgical excision if the PI determines that local dermal irritation may interfere with lesion identification at excision.

Based on remetinostat safety data collected to date in earlier MF-CTCL studies, systemic adverse events are not anticipated.

In the unlikely event that a patient experiences any systemic AE which is consistent with the effects of systemic HDAC inhibition, such as diarrhea or thrombocytopenia **and** the AE is considered possibly related to treatment with remetinostat gel, their treatment will be modified, as follows:

Thrombocytopenia CTC Grade 2 (platelet count ≥ 50 to ≤ 75 x  $10^9$ /L): Reduce treatment frequency of remetinostat gel to BID every second day. Recommence TID daily treatment once platelet count reaches ≥ 75 x  $10^9$ /L. If platelet count does not recover after 2 weeks' every  $2^{nd}$  day dosing, suspend treatment until platelet count reaches ≥ 75 x  $10^9$ /L (maximum period of treatment suspension is 4 weeks).

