Thrombocytopenia CTC Grade ≥ 3 (platelet count ≤ 50 x  $10^9$ /L): Treatment must be discontinued for up to 4 weeks, by which time treatment must be permanently discontinued if the platelet count does not recover to ≥ 75 x  $10^9$ /L. On recovery of platelet count to ≥ 75 x  $10^9$ /L, treatment with remetinostat should initially be re-started BID every second day and then increased to BID daily application if tolerated. If event re-occurs, consider discontinuation of treatment.

**Diarrhea CTC Grade 1, an increase of < 4 stools per day over baseline; mild increase in ostomy output compared to baseline:** Reduce treatment frequency of remetinostat gel to every second day. Recommence BID daily treatment once diarrhea has resolved/returned to baseline status. If diarrhea does not recover after 4 weeks' every second day BID dosing, suspend treatment until diarrhea has resolved/returned to baseline status (maximum period of treatment suspension is 4 weeks).

Diarrhea CTC Grade ≥ 2, an increase of 4 to 6 stools per day over baseline; moderate increase in ostomy output compared to baseline; limiting instrumental activities of daily life (ADL): Treatment must be discontinued for up to 4 weeks, by which time treatment must be permanently discontinued if diarrhea does not resolve/recover to baseline status. Once diarrhea has recovered/returned to baseline status, treatment with remetinostat should initially be re-started BID every second day and then increased to BID daily application if tolerated. If event re-occurs, consider discontinuation of treatment.

If a patient lesion grows by 30% at the 4 week observation point, the patient would be directed to surgery instead of continued therapy on trial.

If 50% of total lesions being treated per protocol have grown, we would stop the study early.

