#### 12.4.1 Analysis Population

We will first analyze the data by intention to treat analysis and then per-protocol analysis by only including tumors ≥ 80% compliant with drug treatment. Tumors with 79% or less compliant with

drug treatment will be reported as a deviation; tumors at least 80% compliant with drug treatment will not be recorded as a deviation. Patients will be instructed to use a band-aid or other form of occlusion. If the patient has difficulty with band-aid usage, the patient may stop and this will be documented.

For subjects who drop out, we will use data from their last study visit if they contribute a biopsy. The analysis population will include participants who have consented to undergo remetinostat treatment and who have at least 1 SCC tumor.

Safety analyses will include all subjects who received at least one dose of study treatment. Graded AEs (number and percent) will be summarized and reported according to the NCI CTCAE v5.0.

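### Section 12.4.1 makes use of a dropout's last caliper reading depend on a biopsy, and the plan gives no ITT response status for a dropout without one

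*Combined protocol and SAP*

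**What the plan says.** **Stopping and leaving.** Section 6 states "Subjects who require discontinuation of treatment for any reason will go" off-study. For Grade 3 or 4 irritation that has not settled within 2 weeks, Table 1 says "treatment should be discontinued, and the patient withdrawn". The text is not uniform. The next sentence in Section 6 reads "The Study Doctor will assess and determine if an individual subject needs to be taken off the study due to side effects", and Section 4.2 treats stopping drug and leaving the study as separate acts: "The investigator has the right to discontinue a patient from study drug or withdraw a patient from the study at any time".

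**Growth.** Under Section 6.1, if a lesion has grown by 30% at Week 4, "the patient would be directed to surgery instead of continued therapy on trial". Under Section 4.2, for a lesion above 20 mm, "such a lesion will be discontinued from treatment (if applicable) and referred for evaluation for surgical resection".

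**Measurement.** The endpoint in Section 12.4 is a decrease of at least 30% in tumor area from baseline to end of study. Section 10.1 specifies calipers. The final reading is at the Week 10 visit, which may fall as late as Week 14. The Study Calendar (Section 9) also marks tumor measurements and photographs in an early-termination column.

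**Analysis.** Section 12.4.1 puts the ITT analysis first and the per-protocol analysis (at least 80% compliance) second. It then says "For subjects who drop out, we will use data from their last study visit if they contribute a biopsy", followed by "The analysis population will include participants who have consented to undergo remetinostat treatment and who have at least 1 SCC tumor". Sections 12.1 and 12.4.2 define the ORR over all eligible and treated tumors. Section 4 takes the research biopsies from those who consent.

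**The concern.** Whether a tissue sample was given says nothing about whether a caliper area is valid, yet the dropout sentence makes one depend on the other. It does not say which biopsy counts: diagnostic, baseline research, or post-treatment. It also does not say what happens to a dropout who lacks it.

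Two applications are open. If the condition acts as an exclusion, tumors leave the ITT denominator for a reason that can be related to outcome, because some stopping follows growth or irritation. Growth-driven stoppers are likely non-responders, so removing them pushes the ORR up, and a single-arm comparison with a fixed 15% has no control arm to offset that. If the condition governs only use of the data, the tumor stays in the denominator, but a measured area is set aside and its response status is left to the analyst. Two analysts following the plan could report different ITT ORRs from the same data.

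**Working it through.** **1. The plan's own figure.** Inputs from Section 12.4.2: n = 30 per-protocol tumors, null ORR 15%, alternative 40%, success at 9 or more responders, one-sided alpha 0.05. Exact binomial:

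- Power = P(X ≥ 9 | 30, 0.40) = 0.906, which matches the stated 91%.
- Attained alpha = P(X ≥ 9 | 30, 0.15) = 0.028. A cutoff of 8 would give 0.070, so 9 is the correct critical value.

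These figures are set on per-protocol tumors and do not depend on the dropout sentence.

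**2. What the plan determines for a dropout.**

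| Dropout tumor | Stays in ITT denominator? | Response status |
|---|---|---|
| Biopsy given | Yes (12.1, 12.4.1, 12.4.2) | From last-visit data |
| No biopsy, early-termination or Week 4 reading exists | Suggested by the denominator wording; the biopsy condition leaves it open | Not stated |
| No biopsy, no post-baseline reading | Same | Not stated |

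**3. Size under an assumption.** The documents give no stopping rate for 1% gel three times daily over 8 weeks. Assume 30 per-protocol tumors plus d = 3 to 6 stopped tumors, one per subject, all non-responders and all without the required biopsy. With x responders, the effect of exclusion is x/30 − x/(30 + d).

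| x | Excluded (x/30) | Counted, d = 3 | Counted, d = 6 | Rise from exclusion |
|---|---|---|---|---|
| 9 | 30.0% | 9/33 = 27.3% | 9/36 = 25.0% | 2.7 to 5.0 points |
| 12 | 40.0% | 12/33 = 36.4% | 12/36 = 33.3% | 3.6 to 6.7 points |

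Exact 90% intervals: 9/30, 16.6% to 46.5%; 9/36, 13.7% to 39.6%; 12/30, 25.0% to 56.6%; 12/36, 20.5% to 48.3%.

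**4. Could the conclusion change?** The plan sets no ITT threshold, so one-sided exact p-values against 15%, P(X ≥ x | n, 0.15), serve only as a reference.

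- x = 9: 0.028 (9/30), 0.0495 (9/33), 0.059 (9/34), 0.080 (9/36).
- x = 10: 0.024 (10/34), 0.035 (10/36).
- x = 12: 0.0008 (12/30), 0.005 (12/36).

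Within this range, 0.05 is crossed only with exactly 9 responders and at least 4 stopped tumors. At a true ORR of 40%, P(X = 9 | 30) = 0.082.

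**The case against.** Much of the case on the other side stands.

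- **Measurement is largely covered.** A reader might infer from the off-study rule that stoppers are never measured again. The Study Calendar does not support that: an early-termination measurement is scheduled, and a lesion that has grown 30% at Week 4 has just been measured. Section 6.1 does not say that such a subject leaves the study.
- **The 20 mm rule works by lesion.** It need not make the subject a dropout, so it is a weak example of the biopsy condition in action.
- **Few tumors may be affected.** Section 4 requires biopsy-proven lesions, says subjects will consent to donate tissue, and allows the later biopsy to be taken at excision. If the dropout sentence means the diagnostic biopsy, almost no one lacks one. The plan does not say, so the number could be near zero.
- **The denominator wording favours inclusion.** A reader might infer that the plan drops these tumors from the ITT analysis. The ITT-first statement, the population sentence and the denominator all point the other way, and a treated tumor with no usable response would naturally add nothing to the numerator. That is an inference, however. The plan does not state it.
- **The illustration is a worst case.** If 2 of 6 stopped tumors had responded, alongside 12 of 30, counting all of them gives 14/36 = 38.9% against 40.0%, a shift of 1.1 points.
- **The decision rule is per-protocol.** Section 10.1.1 also limits the primary-outcome analysis to tumors at 80% compliance or above.

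None of this explains why a caliper reading should need a biopsy, or supplies the missing response status.

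**Conclusion.** The concern holds as a conflict inside Section 12.4.1. A stated rule ties caliper data to an unspecified biopsy, against an ITT-first analysis over all eligible and treated tumors, and the ITT status of a dropout without a biopsy is not given. The effect falls on the ITT estimate: an overstatement of about 3 to 7 points if the condition is applied as an exclusion and 3 to 6 stopped tumors, all non-responders, are added to 30. Those counts are assumptions. The true size cannot be derived from the documents and may be close to nil.

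A reader might go further and infer that the trial's success criterion or power is compromised. That is not supported: both are defined on per-protocol tumors and reproduce as stated, and a changed reading against 15% needs exactly 9 responders with at least 4 stopped tumors within the range examined. The change is still worth making, because it is cheap and removes an analyst's choice from the analysis that the plan names first.

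**What to change.** **Section 12.4.1.** Delete the biopsy condition from the dropout sentence and state:

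- The ITT ORR counts every treated tumor, whether or not a biopsy was given.
- Response is taken from the pre-excision reading or, if there is none, from the early-termination or last post-baseline reading.
- A tumor with no post-baseline reading is a non-responder.
- A sensitivity analysis counts every tumor without a pre-excision reading as a non-responder.

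Report how many tumors fall in each group.

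**Section 6 and Table 1.** State that subjects who permanently stop gel have the early-termination measurement already in the calendar and, unless consent is withdrawn, a caliper reading before their standard-care excision. Nothing here changes when gel is held or stopped, or when surgery is done.

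**Cost.** A few sentences of protocol and analysis text, and a few caliper readings before excisions that would take place anyway. Stoppers' readings will fall at varying times, which the sensitivity analysis helps to show, and the ITT ORR may come out slightly lower. The sample size and the 9-responder rule stay as they are.

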# 6.1. Dose Modifications due to Toxicity and Stopping Criteria

Patients experiencing any treatment-related Grade 3 or higher local dermal irritation will be required to have their treatment exposure suspended until the irritation reduces to at least Grade 2. Guidelines for dose reduction, interruption and discontinuation are provided below:

**Table 1: Dose Modification** 

Grade of Local Dermal Irritation	Defining Clinical Signs	Proposed Treatment Modification			
0 (No Reaction)	None				
1 (Mild)	Definite pink to red coloration	No action required; observation			
2 (Moderate)	Increased redness, with or without edema				
3 (Moderately Severe)	Very red, with edema and vesiculation	Treatment must be suspended until irritation improves to Grade 2 or lower (this must occur within 2 weeks). After the irritation improves to Grade 2 or lower, treatment may be re-started, initially TID every second day, then increased to TID daily, if tolerated. If dermal irritation does not improve to Grade 2 or lower after 2 weeks, treatment should be discontinued, and the patient withdrawn. If event re-occurs, consider discontinuation of treatment.			
4 (Severe)	Deep red, swelling and edema with bullae formation and necrosis	Treatment must be suspended until irritation improves to Grade 2 or lower (this must occur within 2 weeks). After the irritation improves to Grade 2 or lower, treatment may be re-started, initially TID every second day, then increased to TID daily, if tolerated. If dermal irritation does not improve to Grade 2 or lower after 2 weeks, treatment should be discontinued, and the patient withdrawn. If event re-occurs, consider discontinuation of treatment.			

Treatment may be stopped approximately 2 weeks before surgical excision if the PI determines that local dermal irritation may interfere with lesion identification at excision.

Based on remetinostat safety data collected to date in earlier MF-CTCL studies, systemic adverse events are not anticipated.

In the unlikely event that a patient experiences any systemic AE which is consistent with the effects of systemic HDAC inhibition, such as diarrhea or thrombocytopenia **and** the AE is considered possibly related to treatment with remetinostat gel, their treatment will be modified, as follows:

Thrombocytopenia CTC Grade 2 (platelet count ≥ 50 to ≤ 75 x  $10^9$ /L): Reduce treatment frequency of remetinostat gel to BID every second day. Recommence TID daily treatment once platelet count reaches ≥ 75 x  $10^9$ /L. If platelet count does not recover after 2 weeks' every  $2^{nd}$  day dosing, suspend treatment until platelet count reaches ≥ 75 x  $10^9$ /L (maximum period of treatment suspension is 4 weeks).

Thrombocytopenia CTC Grade ≥ 3 (platelet count ≤ 50 x  $10^9$ /L): Treatment must be discontinued for up to 4 weeks, by which time treatment must be permanently discontinued if the platelet count does not recover to ≥ 75 x  $10^9$ /L. On recovery of platelet count to ≥ 75 x  $10^9$ /L, treatment with remetinostat should initially be re-started BID every second day and then increased to BID daily application if tolerated. If event re-occurs, consider discontinuation of treatment.

**Diarrhea CTC Grade 1, an increase of < 4 stools per day over baseline; mild increase in ostomy output compared to baseline:** Reduce treatment frequency of remetinostat gel to every second day. Recommence BID daily treatment once diarrhea has resolved/returned to baseline status. If diarrhea does not recover after 4 weeks' every second day BID dosing, suspend treatment until diarrhea has resolved/returned to baseline status (maximum period of treatment suspension is 4 weeks).

Diarrhea CTC Grade ≥ 2, an increase of 4 to 6 stools per day over baseline; moderate increase in ostomy output compared to baseline; limiting instrumental activities of daily life (ADL): Treatment must be discontinued for up to 4 weeks, by which time treatment must be permanently discontinued if diarrhea does not resolve/recover to baseline status. Once diarrhea has recovered/returned to baseline status, treatment with remetinostat should initially be re-started BID every second day and then increased to BID daily application if tolerated. If event re-occurs, consider discontinuation of treatment.

If a patient lesion grows by 30% at the 4 week observation point, the patient would be directed to surgery instead of continued therapy on trial.

If 50% of total lesions being treated per protocol have grown, we would stop the study early.

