# 2.4 Study Design

# For clinicaltrials.gov and Stanford Clinical Trials Directory compliance (see Section 10 for additional information)

- The primary purpose of this study is:
  - To determine if 8 weeks of topical remetinostat gel applied TID under occlusion will suppress SCC growth
  - To determine the overall response rate (ORR) of SCCs after 8 weeks of treatment with topical remetinostat gel 1%, as measured by at least 30% decrease in greatest area (in mm²).
- Subjects with at least 1 biopsy-proven cutaneous SCC will be recruited for this study.
- Subjects will apply remetinostat gel 1% to at least 1 SCC.
- Non-invasive cutaneous SCC lesions, including Bowen's disease, are also eligible for this study
- There is 1 treatment option: Topical remetinostat gel 1% applied 3 times daily.
- The study is a single-arm, open-label design
- For purposes of ClinicalTrials.gov, there is no secondary outcome.

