#### 4. TREATMENT PLAN

Adult subjects in the clinic who have one or more biopsy-proven cutaneous SCC or SCC-in situ (hereafter referred to as "SCC") lesions greater than or equal to 5 mm in diameter, at least one of which is being biopsied as a normal course of care, will be invited to participate in this trial. Eligibility of prospective participants will be confirmed, and subjects will enroll according to stated inclusion and exclusion criteria.

Screening visits may be combined with or without day 1 visit.

Prospective participants must be willing to sign a consent form. Subjects will also give consent to donate their SCC tissue for biomarker measurement and apply medication 3-times daily under bandage occlusion for 8 weeks. The anticipated bandage will be an adhesive bandage (e.g., "Band-Aid") with a non-adherent dressing, or paper tape with a non-adherent dressing.

Drug treatment: Subjects will be instructed to apply topical remetinostat to individual SCCs 3-times daily (TID) for 8 weeks. Patients will be asked to discontinue application of the medication at 8 weeks, approximately 2 weeks prior to their surgical excision(s), as dermal irritation from study drug may interfere with lesion identification at excision.

At least 1 target SCC will be identified requiring surgical excision per standard of care. In addition to being measured and photographed, this lesion(s) may be biopsied. Week 8 biopsy may be collected at the time of surgical excision of lesion(s). Histopathological evaluation of the specimen may be performed.

After an initial treatment application demonstration by the study team, treatment applications will be self-administered by the subject or a caregiver. Patients will receive oral and written administration instructions at the outset of the trial as follows:

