#### **STUDY DRUG INSTRUCTIONS:**

Study Drug: Remetinostat 1% gel

How Much: Apply a thin layer over the tumor(s) identified by the

study doctor.

How Often: Three times daily.

When: You should apply the gel in the morning, at mid-day, and in

the evening.

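### Section 6.1 resumes dosing after Grade 1 diarrhea at twice daily in a three-times-daily trial, and its platelet bands overlap at exactly 50 and 75 x 10^9/L

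*Combined protocol and SAP*

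**What the plan says.** Section 2.4 (Study Design) allows a single regimen: "There is 1 treatment option: Topical remetinostat gel 1% applied 3 times daily". Section 4 (Treatment Plan) repeats it: "Subjects will be instructed to apply topical remetinostat to individual SCCs 3-times daily (TID) for 8 weeks". The patient diary in Appendix A agrees: "How Often: Three times daily".

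The text after Table 1 in section 6.1 gives four rules for systemic adverse events. They apply only where the event is consistent with systemic HDAC inhibition and is also considered possibly related to the gel.

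- **Grade 1 diarrhea:** reduce to alternate-day dosing (described later in the same rule as twice daily, BID, on those days), then "Recommence BID daily treatment once diarrhea has resolved/returned to baseline status".
- **Grade 2 thrombocytopenia:** reduce to BID on alternate days, then "Recommence TID daily treatment once platelet count reaches" 75 x 10^9/L or more.
- **Grade 3 or higher thrombocytopenia and Grade 2 or higher diarrhea:** stop for up to four weeks. On recovery, treatment is initially "re-started BID every second day and then increased to BID daily application if tolerated".

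The two platelet bands are "Thrombocytopenia CTC Grade 2 (platelet count ≥ 50 to ≤ 75 x" 10^9/L) for the reduce rule and "Thrombocytopenia CTC Grade ≥ 3 (platelet count ≤ 50 x" 10^9/L) for the stop rule. Recovery is a count of 75 x 10^9/L or more in both.

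**The concern.** To recommence is to go back to something, and the schedule before the event was TID. The Grade 1 diarrhea sentence names a different schedule without saying that the dose is being lowered for good. Two investigators could therefore treat the same patient differently, each with a defensible reading. The outcome also sits oddly beside the neighbouring rules: the mildest systemic event covered ends at a lower frequency than Grade 2 thrombocytopenia or Grade 4 skin irritation, both of which may return to TID daily.

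The platelet rules have a plainer fault. Both bands include the value 50, and the two rules call for different actions there: carry on at a reduced frequency, or stop. The value 75 belongs to the band that triggers a reduction and also meets the threshold that ends one.

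What is at stake is clear and consistent dosing instructions for a patient with a suspected systemic effect. The primary analysis does not turn on it.

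**Working it through.** **The plan's own figure.** Sections 12.1, 12.4.2 and 12.6.2 state 91% power with 30 tumors and at least 9 responders, for response rates of 15% against 40%.

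- Power: P(X ≥ 9 | n = 30, p = 0.40) = 0.906, which reproduces 91%.
- Type I error: P(X ≥ 9 | n = 30, p = 0.15) = 0.0278, within the one-sided 0.05. A cut-off of 8 would give 0.0698, so 9 is right.

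Neither calculation uses the dosing rules, so nothing below changes it.

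**Restart frequency, rule by rule (section 6.1 and Table 1).**

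| Event | Action | Frequency on recovery | Word used |
|---|---|---|---|
| Skin irritation, Grade 3 or 4 | Suspend | TID alternate days, then TID daily | restart |
| Thrombocytopenia, Grade 2 | BID alternate days | TID daily | recommence |
| Diarrhea, Grade 1 | Alternate days | BID daily | recommence |
| Thrombocytopenia, Grade ≥ 3 | Stop | BID alternate days, then BID daily | restart, then increase |
| Diarrhea, Grade ≥ 2 | Stop | BID alternate days, then BID daily | restart, then increase |

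The second and third rows are the close parallel: a reduce-only action followed by *recommence*. One returns to the trial regimen and the other does not.

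**Size of the difference.** TID daily is 3 x 7 = 21 applications a week. BID daily is 2 x 7 = 14. The ratio is 14/21 = 0.667, or two-thirds of the planned frequency for as long as treatment continues.

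**Platelet bands.** Each count (x 10^9/L) is tested against reduce (50 to 75, both ends included), stop (50 or less) and recovered (75 or more):

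| Count | As written | With Grade 2 ≥ 50 to < 75 and Grade ≥ 3 < 50 |
|---|---|---|
| 49.9 | stop | stop |
| 50 | reduce and stop | reduce |
| 50.1 | reduce | reduce |
| 74.9 | reduce | reduce |
| 75 | reduce and recovered | recovered |
| 75.1 | recovered | recovered |

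The revised bands remove both overlaps, leave no gap and keep the protocol's recovery threshold.

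**How often the rules might be used.** Section 2.2 reports no related systemic adverse event in either CTCL study. The phase 1 study had 3 cohorts x 5 = 15 patients on active gel and the phase 2 study had 60, so 0 of 75. The one-sided 95% upper limit is 1 - 0.05^(1/75) = 0.039, and 0.0392 x 40 subjects = 1.6. This is a loose limit for any related systemic event, not for Grade 1 diarrhea alone. It rests on assuming that the CTCL rate carries over, although those patients used at most BID and some used 0.1% or 0.5% gel. The basal cell carcinoma study in section 2.2 used the 1% gel TID under occlusion. For its 14 completed tumors it lists only skin reactions and application-site pain, though the list may not be exhaustive.

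**The case against.** The best defence is that BID was meant. Three of the four systemic rules end at BID daily, and the Grade 1 diarrhea rule mentions BID twice. The rules apply only when the event may be due to the gel, so a lasting step down after suspected systemic exposure is a reasonable safety choice. The highest regimen in the CTCL phase 2 study was 1% BID, so BID is a frequency with some safety experience.

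Much of this stands. The documents do not reveal the intent, which is why the TID correction should give way if the sponsor confirms a step-down. It does not rescue the sentence as written, because a deliberate reduction would still need to be stated. Nor does the alternate-day BID step settle the matter: the Grade 2 platelet rule uses the same step and returns to TID.

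On platelets, the defence is that section 4 schedules no laboratory tests beyond a pregnancy test, that section 6.1 calls its rules guidelines, and that the investigator may stop the drug at any time. That limits how often the overlap could matter, but it does not say which rule governs at 50.

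A reader might go further and infer that the patient is underdosed. Nothing in the documents shows that BID is inadequate for SCC; they support only that it is below the planned frequency. A reader might also infer that such a tumor falls below the 80% compliance cut-off and leaves the per-protocol set. Sections 10.1.1 and 12.4.1 do not say whether applications are counted against the planned TID course or the course as modified under section 6.1. Under the second reading, a patient who follows the instructions is fully compliant, so the loss cannot be claimed.

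**Conclusion.** Section 6.1 holds two internal inconsistencies, both visible in the current text. The Grade 1 diarrhea rule resumes at BID in a TID-only trial, two-thirds of the planned frequency, with no lasting reduction stated. The platelet bands overlap at exactly 50 and exactly 75 x 10^9/L, and at 50 the two rules conflict.

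Confidence is high that the wording is inconsistent. It is not high that BID was a slip, since intent is unstated. The BID restarts after Grade 3 or higher thrombocytopenia and Grade 2 or higher diarrhea are worded as a restart followed by an increase. They can be read as deliberate, so they are questions and not errors.

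The point is minor. Section 6.1 does not anticipate systemic events, platelets are not routinely measured, section 12.4.1 puts the intention-to-treat analysis first, and the power is unchanged. No effect on the trial's conclusion is shown.

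**What to change.** In section 6.1:

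1. Write the platelet bands as Grade 2: ≥ 50 to < 75 x 10^9/L, and Grade ≥ 3: < 50 x 10^9/L. Keep recovery at ≥ 75.
2. In the Grade 1 diarrhea rule, change the restart from BID daily to TID daily, unless the sponsor confirms that a lasting step-down to BID is intended. In that case replace *recommence* with an explicit statement that the frequency is reduced to BID for the rest of treatment.
3. In the same query, ask whether the BID restarts after Grade ≥ 3 thrombocytopenia and Grade ≥ 2 diarrhea are intended lasting reductions. If so, say so; if not, correct them to TID.

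The cost is a few words and one question to the sponsor, with no added visit, test or patient. The one real downside is that a TID restart gives more exposure than BID after a mild systemic event possibly caused by the gel, which is why the sponsor should be able to choose the step-down.
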